6.5 Exploratory Analysis

(1) Logistic regression

The exploratory analysis will focus on identifying the potential predictors for the clinical effectiveness of adalimumab (persistent clinical response at weeks 8 and 56, clinical response at weeks 8 and 56, clinical remission, clinical response without steroid administration, clinical remission without steroid administration, mucosal healing, and below 250 fecal calprotectin level).

To confirm the predictors, univariate logistic regression will be performed for each factor, and then multiple logistic regressions will be performed for the significant predictors.

Here, the independent variables shown below will be considered predictors, but the variables to be used in the actual analysis can be added or subtracted considering the collected data and characteristics.

- Gender
- Onset age
- **BMI**
- Disease duration
- Full Mayo score
- Fecal calprotectin level
- UC extent
- CRP
- Albumin
- Trough level of adalimumab
- Concomitant medication for UC
- TNF antagonist naivety
- Dose escalation
- (2) Percentage of subjects according to the fecal calprotectin level at baseline, visit 2 (week 8), and visit 8 (week 56)

The frequency and percentage of subjects with a below 250 fecal calprotectin level at baseline, visit 2

^a Adverse drug reaction (ADR): Adverse events with "probable," "possible," "probably not," or "not assessable" causality

^b PTYs = Sum of the total administration period (days) of all the subjects / 365.25

[°] AE incidence rate per 100 PTY = {(Number of AEs)/(PTYs)}×100

| dreamcis A TIGERMED COMPANY | | Last Update Date |
|----------------------------------|---|------------------|
| | CONFIDENTIAL: | |
| | THIS DOCUMENT AND THE INFORMATION CONTAINED HEREIN ARE PROPRIETARY TO THE COMPANY AND ARE NOT TO BE DISCLOSED | 02-NOV-2018 |
| | WITHOUT THE WRITTEN PERMISSION OF THE COMPANY. | |
| STATISTICAL ANALYSIS PLAN (V2.0) | | |

STATISTICAL ANALYSIS PLAN (V2.0

(week 8), and visit 8 (week 56) will be presented.

(3) Percentage of subjects according to the CRP level at baseline, visit 2 (week 8), and visit 8 (week 56)

The frequency and percentage of subjects with a CRP level of below 5 mg/L at baseline, visit 2 (week 8), and visit 8 (week 56) will be presented.

(4) Clinical response at each visit depending on the TNF antagonist naivety

The frequency and percentage of subjects who showed a clinical response at visit 2 (week 8) will be presented by classifying the subjects into two groups depending on the TNF antagonist naivety, and the 95% confidence interval for the result will be calculated. Additionally, the frequency and percentage of subjects who showed a persistent clinical response at visit 2 (week 8), visit 4 (week 24), and visit 8 (week 56) will be presented for each group, and the 95% confidence interval for the result will be calculated. Chi-square test or Fisher's exact test will be performed to determine if there is a difference in the clinical response rate between the two groups.

(5) Clinical remission at each visit depending on the TNF antagonist naivety

The frequency and percentage of subjects who showed clinical remission at visit 2 (week 8) will be presented by classifying the subjects into two groups depending on the TNF antagonist naivety. Among the subjects who showed a clinical response at visit 2 (week 8), the frequency and percentage of those who showed clinical remission at visit 4 (week 24) and visit 8 (week 56) will also be presented for each group. Chi-square test or Fisher's exact test will be performed to check if there is a difference in the clinical remission rate between the two groups.

(6) Clinical response without steroid administration at each visit depending on the TNF antagonist naivety

The frequency and percentage of subjects who showed a clinical response without steroid administration at visit 2 (week 8) will be presented by classifying the subjects into two groups depending on the TNF antagonist naivety. Among the subjects who showed a clinical response at visit 2 (week 8), the frequency and percentage of those who showed a clinical response without steroid administration at visit 4 (week 24) and visit 8 (week 56) will also be presented for each group. Chi-square test or Fisher's exact test will be performed to determine if there is a difference in the clinical response rate without steroid

| | | Last Update Date |
|----------------------------------|---|------------------|
| dreamcis ATIGERMED COMPANY | CONFIDENTIAL: THIS DOCUMENT AND THE INFORMATION CONTAINED HEREIN ARE PROPRIETARY TO THE COMPANY AND ARE NOT TO BE DISCLOSED. | 02-NOV-2018 |
| | WITHOUT THE WRITTEN PERMISSION OF THE COMPANY. | 02 1.0 . 2010 |
| STATISTICAL ANALYSIS PLAN (V2.0) | | |

administration between the two groups.

(7) Clinical remission without steroid administration at each visit depending on the TNF antagonist naivety

The frequency and percentage of subjects who showed clinical remission without steroid administration at visit 2 (week 8) will be presented by classifying the subjects into two groups depending on the TNF antagonist naivety. Among the subjects who showed a clinical response at visit 2 (week 8), the frequency and percentage of those who showed clinical remission without steroid administration at visit 4 (week 24) and visit 8 (week 56) will also be presented for each group. Chi-square test or Fisher's exact test will be performed to determine if there is a difference in the clinical remission rate without steroid administration between the two groups.

(8) Mucosal healing at each visit depending on the TNF antagonist naivety

The frequency and percentage of subjects who showed mucosal healing at visit 2 (week 8) will be presented by classifying the subjects into two groups depending on the TNF antagonist naivety. Among the subjects who showed a clinical response at visit 2 (week 8), the frequency and percentage of those who showed mucosal healing at visit 8 (week 56) will also be presented for each group. Chi-square test or Fisher's exact test will be performed to determine if there is a difference in the mucosal healing rate between the two groups.

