6.2 Demographic Characteristics

Descriptive statistics will be obtained for the demographic data and health status in the ITT set. For the continuous data, the mean, standard deviation, median, 1st quartile, 3rd quartile, minimum, and maximum values will be obtained, while for the categorical data, the frequencies and percentages will be calculated.

The variables representing demographic data are as follows:

- (1) Continuous Data
- <Basic and Disease Information>
 - Age (years)
 - Onset age (years)^a
 - Height (cm)
 - Weight (kg)
 - BMI (kg/m²)
 - Disease duration (months)^b
 - Full Mayo score (endoscopic findings, stool frequency, rectal bleeding, physician's global assessment) at baseline
 - Initial fecal calprotectin level
 - Laboratory tests (hemoglobin (g/dl), albumin (g/dl), ESR (mm/hr), CRP (mg/dl))
 - Adalimumab trough level (μg/mL)^c
 - Antibody adalimumab (μg/mL)^d

<Medication Administration Information>

- Total administration period (days)^e
- Total administration frequency (times)
- Total administration dose (mg)
- Period to dose escalation (days)^f

| -4 | | Last Update Date |
|-------------------|--|------------------|
| | CONFIDENTIAL: | |
| dreamcis | THIS DOCUMENT AND THE INFORMATION CONTAINED HEREIN ARE | 00 31031 0010 |
| ATIGERMED COMPANY | PROPRIETARY TO THE COMPANY AND ARE NOT TO BE DISCLOSED | 02-NOV-2018 |
| | WITHOUT THE WRITTEN PERMISSION OF THE COMPANY. | |
| CTATICTICA | I ANALVOIC DI AN (V/) () | |

STATISTICAL ANALYSIS PLAN (V2.0)

(2) Categorical Data

<Basic and Disease Information>

- Gender (male/female)
- Age (19-29 years / 30-39 years / 40-49 years / 50-59 years / \geq 60 years)
- Family history of UC (yes / no / unknown)
- UC extent (proctitis / left-sided colitis / extensive colitis / others)
- Co-morbidities (yes/no/unknown) and details⁹
- Study completion (yes/no) and reason for study discontinuation (loss of follow-up/inadequate response/ withdrawal of patient consent/others)

<Medication Administration Information>

- Previous medication for UC (yes/no/unknown) and details

 (Systemic steroids/antibiotics/non-biologics (5-ASA/methotrexate/azathioprine/6-mercaptopurine/cyclosporine/tacrolimus) / biologics^h (1 medication / 2 medication and above) / others)
- Concomitant medication for UC (yes/no) and details^g
 (5-ASA / methotrexate / azathioprine / 6-mercaptopurine / cyclosporine / tacrolimus / steroid (20 mg and above (daily dose) / less than 20 mg (daily dose))
- Administration status

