 (First dose (80/160 mg), second dose (40mg/80mg), dose escalation (yes/no), administration frequency
 (2 times and below / more than 2 times), reason for discontinuation (inadequate response / adverse event / others))
- TNF antagonist naivety (yes/no)
- * The categories can be modified according to the structure and characteristics of the collected data.

^a Onset age: The period from the date of birth to the date of diagnosis

^b Disease duration: The period from the date of diagnosis to the date of consent of the subject

 $^{^{}c}$ Adalimumab trough level: The below the quantification limit (BQL) value of the adalimumab trough level is <0.040 μ g/mL. If collected like this, it is analyzed by replacing it with 0.040 μ g/mL, and the total number of replacements will be specified.

d Antibody adalimumab: The below the quantification limit (BQL) value of antibody adalimumab will be confirmed at the central lab after the final data collection is completed. The data at the BQL will be analyzed by replacing them with the lowest measurable value, and the total number of replacements will be specified.

^e Total administration period: It is calculated as the period from the administration start date to the administration end date, and if administration is ongoing, the administration end date is replaced with the last visit date.

^f Period to dose escalation: The period from the administration start date to the first dose escalation (every 1 week)

| dreamcis ATIGERMED COMPANY | | Last Update Date |
|-------------------------------|--|------------------|
| | CONFIDENTIAL: THIS DOCUMENT AND THE INFORMATION CONTAINED HEREIN ARE | |
| | PROPRIETARY TO THE COMPANY AND ARE NOT TO BE DISCLOSED | 02-NOV-2018 |
| | WITHOUT THE WRITTEN PERMISSION OF THE COMPANY. | |
| STATISTICA | LANALYSIS PLAN (V2 0) | |

^g The classification of the co-morbidities and concomitant medications for UC is presented with the terms classified based on the dictionary specified in the latest version of DMP. Here, the co-morbidities and concomitant medications are summarized with the system organ class (SOC) and preferred term (PT) based on the MedDRA classification. The concomitant medications for UC are summarized with anatomical

h Biologics: Single-dose infliximab or a single dose of another medication is classified as 1 medication, and if infliximab and another medication are both administered, it is classified as 2 medications and above.

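### SAP 6.5(1) offers an undated dose-escalation flag as a predictor of week-8 outcomes, although on scheduled visits escalation cannot precede the week-8 assessment

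*SAP*

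**What the plan says.** SAP 6.5(1) runs logistic regressions for a set of outcomes that begins "persistent clinical response at weeks 8 and 56, clinical response at weeks 8 and 56, clinical remission" and continues with the steroid-free endpoints, mucosal healing and low fecal calprotectin. Remission, the steroid-free endpoints and mucosal healing carry no visit there, but SAP 4.1.2 places them at weeks 8 and 56.

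One predictor list serves all of these outcomes: "the independent variables shown below will be considered predictors, but the variables to be used in the actual analysis can be added or subtracted". Its thirteenth and last entry is "Dose escalation", with no time point. Selection is by screening: "univariate logistic regression will be performed for each factor, and then multiple logistic regressions will be performed for the significant predictors".

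The only coding of the variable is in SAP 6.2, under administration status: "dose escalation (yes/no", again without a cut-off date. SAP 6.2 separately derives a time to escalation, defined as "The period from the administration start date to the first dose escalation (every 1 week" interval dosing, but 6.5(1) does not use it.

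Protocol 9.3 (Blood samples) ties escalation to inadequate response, defined by partial Mayo scores on two consecutive visits at least 14 days apart. Protocol 9.1 schedules visits at baseline and at weeks 8, 16, 24, 32, 40, 48 and 56, each with a window of one week either way. The protocol's own lists of candidate predictors (9.1, 9.3 and 9.7.2) do not include dose escalation.

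**The concern.** A variable that takes its value after an outcome cannot predict that outcome. If the SAP list is applied as written, week-8 response is regressed on a flag that, on the planned visits, is set at week 8 or later.

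The flag also need not be neutral. Protocol 9.1 describes week-8 responders as the subjects who continue on treatment and are followed. Under Protocol 9.2.2, stopping adalimumab means drop-out with no further data, apart from the reason and serious adverse events. A subject who stops after week 8 can therefore never be recorded as escalated later. Response at week 8 then affects the chance of being flagged, and the regression would report that as escalation predicting response. If significant in the univariate screen, the flag goes on into the multiple model.

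What is at stake is the credibility of the week-8 predictor models. Exploring predictive factors is part of the stated objective (Protocol 8.0, SAP 2.2), and 6.5(1) is the only regression analysis of predictors in the SAP.

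**Working it through.** **Timing.** Inputs: the two-visit trigger (Protocol 9.3), and the visit schedule and window (Protocol 9.1).

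- Both qualifying visits after baseline: the first scheduled pair is weeks 8 and 16. Earliest escalation = week 16, or 16 − 1 = week 15 with the window.
- Baseline counted as one of the two: the pair is weeks 0 and 8. Earliest escalation = the week-8 visit itself.

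On neither reading does escalation precede the week-8 assessment. Only unscheduled visits before week 8 could change this, and the documents neither plan them nor rule them out.

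**Illustrative size.** The documents give no escalation rate, so the counts of escalated subjects are assumptions. The other inputs come from Protocol 9.5: 147 subjects, 5% drop-out, 75% response.

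The plan's own figure can be reproduced. At 75% response, the smallest n whose exact (Clopper-Pearson) 95% interval is no wider than 15 percentage points is 139, and 139 / 0.95 = 146.3, rounded up to 147. Taking 139 evaluable: 139 × 0.75 = 104.25, so 104 responders and 35 non-responders.

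*All k escalated subjects are week-8 responders.* The table is [k, 0; 104 − k, 35]. One cell is zero, so the odds ratio is not finite.

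| k escalated | Fisher p | Likelihood-ratio p |
|---|---|---|
| 5 | 0.33 | 0.085 |
| 10 | 0.066 | 0.014 |
| 12 | 0.037 | 0.007 |
| 15 | 0.012 | 0.002 |
| 20 | 0.004 | 0.0004 |

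Fisher p first drops below 0.05 at k = 12; the likelihood-ratio p does so at k = 7. The Fisher threshold is 9 if response is 65% (90 and 49 subjects) and 20 if it is 85% (118 and 21). SAP 6.5(1) does not name the test used in the screen. At k = 10, Fisher and likelihood ratio fall on opposite sides of 0.05, and a Wald test from a logistic fit stopped at 25 iterations gives p of about 1.00.

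*Some escalated subjects are non-responders.* With b non-responders among k escalated, OR = (k − b)(35 − b) / [b(104 − k + b)].

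| k | b | Odds ratio | Fisher p |
|---|---|---|---|
| 10 | 1 | 9 × 34 / (1 × 95) = 3.2 | 0.45 |
| 15 | 1 | 14 × 34 / (1 × 90) = 5.3 | 0.12 |
| 20 | 1 | 19 × 34 / (1 × 85) = 7.6 | 0.025 |
| 10 | 2 | 8 × 33 / (2 × 96) = 1.4 | 1.00 |
| 20 | 2 | 18 × 33 / (2 × 86) = 3.5 | 0.10 |
| 20 | 5 | 15 × 30 / (5 × 89) = 1.01 | 1.00 |

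The association weakens quickly and is gone once non-responders make up the overall 25% of escalated subjects (5 of 20).

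**Direction.** If baseline counts and the trigger is met at the week-8 visit, the partial Mayo score has not improved, or is still at least 7 from a baseline of 8 or 9. Most such subjects would be week-8 non-responders, and the association would run the other way. The time-order problem is the same.

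**The case against.** The strongest reply is that the SAP already leaves room to deal with this: "the variables to be used in the actual analysis can be added or subtracted considering the collected data and characteristics". That clause does let the analyst drop the flag without an amendment. But it does not require removal, sets no timing rule, and leaves the choice until the data are in.

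Second, the timing argument rests on scheduled visits. A 14-day minimum gap does little work between visits eight weeks apart, so closer unscheduled visits may have been in mind. Protocol 9.3 also provides for endoscopy at inadequate response as well as at the fixed visits. This stands as a qualification: an escalation before week 8 is possible. It does not rescue an undated flag, which would mix any such early escalations with later ones.

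Third, the illustrative p-values need almost all escalated subjects to be responders. That is fair. Protocol 9.1 says responders may continue, and Protocol 9.2.2 does not list week-8 non-response as a reason for drop-out, so escalated non-responders cannot be excluded. The tables show what can happen; they are not a forecast.

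A reader might go further and infer that the SAP defines a whole-study flag. It does not: the window is simply unspecified. A reader might also infer that escalation is misplaced in the week-56 models. The documents do not support that: there escalation can precede the outcome and be a legitimate prognostic marker, and 6.5(1) makes no causal claim about it. Nor do they support a blanket rule that every predictor be measured before its outcome. The protocol itself names week-8 calprotectin, microbiota and trough level as candidate factors, and such a rule would remove them from the week-8 models.

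**Conclusion.** The point holds for the week-8 models only. As written, SAP 6.5(1) allows week-8 outcomes to be regressed on an undated escalation flag that, on scheduled visits, is set at week 8 or later. That conclusion follows from the trigger and the visit schedule and does not depend on the illustrative figures.

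Neither the size nor the direction of the resulting association can be fixed from the documents. Both depend on the unknown number of escalations, on how many occur in week-8 non-responders, and on whether baseline counts as one of the two trigger visits.

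The point is minor. It affects one of 13 covariates in an exploratory analysis. Primary estimates and sample size are unaffected, no error is claimed for week-56 outcomes, and no view is taken on the escalation rule itself.

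**What to change.** In SAP 6.5(1), remove dose escalation from the predictors of all week-8 outcomes. Alternatively, count a subject as escalated in those models only when the time to first escalation, already derived in SAP 6.2, places it before that subject's week-8 assessment.

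Keep the protocol's prespecified baseline and week-8 factors. Escalation may stay in the list for week-56 outcomes as a prognostic marker.

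The cost is a change of SAP wording, with no new data. The downside is a few fewer exploratory odds ratios.

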2.4 Study Size

The primary endpoint of this study is to investigate the effectiveness of adalimumab in Korean patients with Ulcerative Colitis (UC) in real life settings. With reference to adalimumab real life data in UC, clinical response rate to adalimumab at week 12 was about 75% (10). Assuming 95% confidence interval, 15% confidence interval width and an estimated drop-out rate of 5%, we aim to recruit up to 147 subjects in this study.

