5.2 Safety Assessment

An adverse event (AE) is defined as an unusual medical event that occurred in a subject, and is not necessarily causally related to the drug. Therefore, AEs are undesirable and unintended signs (including abnormal clinical test values), symptoms, or temporary illnesses, regardless of the causality with the use of the drug.

Such AEs may not only be due to unintentional or intentional overdose, drug abuse, and discontinuation of the drug but may also be caused by the use of a drug in accordance with the authorization details within the product instruction. Deterioration of the existing disease and conditions is also considered an AE.

6. Statistical Analysis Methods

All statistical analyses will be performed with the SAS software version 9.4 or higher. For all the statistical tests, two-sided tests will be conducted at the 0.05 significance level. Where applicable, an analytical method will be employed depending on whether or not to satisfy the normality assumptions.

For the continuous variables, the number of subjects, mean, standard deviation, median, 1st quartile, 3rd quartile, minimum, and maximum values will be presented. For the categorical variables, the frequency and percentage will be presented. The figures with decimal places, such as the mean, standard deviation, and percentage, will be rounded off to the second decimal place, and the p-value will be rounded off to the fourth decimal place.

| dreamcis ATIGERMED COMPANY | | Last Update Date |
|----------------------------------|---|------------------|
| | CONFIDENTIAL: THIS DOCUMENT AND THE INFORMATION CONTAINED HEREIN ARE PROPRIETARY TO THE COMPANY AND ARE NOT TO BE DISCLOSED. | 02-NOV-2018 |
| | WITHOUT THE WRITTEN PERMISSION OF THE COMPANY. | 02 110 7 2010 |
| STATISTICAL ANALYSIS PLAN (V2.0) | | |

When day is converted to month, it will be based on 30 days per month.

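### The week-24 and week-56 comparisons of TNF-naive with TNF-experienced patients in SAP 6.5(5)-(8) are made only among week-8 responders, so they describe maintenance of effect and can miss a difference that acts through week-8 response

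*SAP*

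**What the plan says.** SAP 6.5 gives TNF antagonist naivety its own run of analyses, items (4) to (8).

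- **Item (4), clinical response.** After the week-8 rate, "subjects who showed a persistent clinical response at visit 2 (week 8), visit 4 (week 24), and visit 8 (week 56) will be presented" separately by naivety. The text names no denominator for this. SAP 6.3.1 defines persistent response so that week-8 response is part of it.
- **Item (5), remission.** The week-8 percentage has no restriction. For the later visits the denominator becomes the week-8 clinical responders, and "those who showed clinical remission at visit 4 (week 24) and visit 8 (week 56) will also be presented for each group". Then "Chi-square test or Fisher's exact test will be performed to check if there is a difference in the clinical remission rate between the two groups".
- **Items (6) and (7), steroid-free response and steroid-free remission.** Same structure and same responder denominator at weeks 24 and 56.
- **Item (8), mucosal healing.** Among week-8 responders, "those who showed mucosal healing at visit 8 (week 56) will also be presented for each group". There is no week-24 analysis.

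The opening of SAP Section 6 says that "two-sided tests will be conducted at the 0.05 significance level". SAP 2.5.1 defines the ITT set at week 56 as the week-8 responders. SAP 6.5(1) lists naivety among the candidate predictors, and week-8 response among the outcomes to be predicted. No power, effect size or naive/experienced split is given for these tests.

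**The concern.** Naivety is a baseline characteristic and week-8 response comes after it. If prior anti-TNF exposure lowers the chance of responding by week 8, restricting the later comparison to responders removes that part of the difference. The experienced patients who remain are also a more selected group than the naive patients who remain.

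The result answers a legitimate question: given an early response, is it maintained equally well in both groups? It does not answer whether naive and experienced patients who start adalimumab end up with different outcomes. The item titles speak of each visit by naivety and do not make that distinction.

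Finding predictors of response is part of the study objective (SAP 2.2), and naivety is the only predictor with its own block of analyses. A null responder-only result at week 56 could be read as showing that prior anti-TNF use has no bearing on long-term outcome, when the two groups differ among all treated.

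**Working it through.** **Sample size stated in the plan.** SAP 2.4 reports that "clinical response rate to adalimumab at week 12 was about 75"%, then "Assuming 95% confidence interval, 15% confidence interval width and an estimated drop-out rate of 5"%, and "we aim to recruit up to 147 subjects in this study". With an exact (Clopper-Pearson) 95% interval at a proportion of 0.75, the smallest n with full width no more than 0.15 is 139 (width 0.14999). Then 139 / 0.95 = 146.3, which rounds up to 147. The plan's figure reproduces, but it was set to estimate one overall rate and not to compare naive with experienced patients.

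**Inputs.** From the documents: 139 evaluable, two-sided 0.05, chi-square or Fisher test. Assumed, because the documents do not give them: 60% naive, so 83 naive and 56 experienced; week-8 response r in each group; remission q among responders in each group. Dropout after week 8 is ignored.

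**Rates.** With week-8 non-responders counted as not in remission, the all-treated rate in a group is r × q. The responder-only rate is q.

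**A difference that acts only through week-8 response.** Take r = 0.80 and 0.65, and q = 0.50 in both groups.

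- Responder-only: 50% versus 50%, difference 0.
- All treated: 0.80 × 0.50 = 40.0% versus 0.65 × 0.50 = 32.5%, difference 7.5 points.

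**Power.** The formula is the pooled-variance normal approximation to the chi-square test:

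power = Φ[(|p1 − p2| − 1.96 × SE0) / SE1]

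Here SE0 = √[p̄(1 − p̄)(1/n1 + 1/n2)] and SE1 = √[p1(1 − p1)/n1 + p2(1 − p2)/n2]. Remission among responders is set at 50% versus 30%.

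Week-8 response 80% / 65%:

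- All treated, n = 83 and 56: 40.0% versus 19.5%, p̄ = 0.317, SE0 = 0.0805, SE1 = 0.0755. (0.205 − 0.158) / 0.0755 = 0.63, so power is 73%.
- Responders, n = 66.4 and 36.4: 50% versus 30%, p̄ = 0.429, SE0 = 0.1021, SE1 = 0.0976. (0.200 − 0.200) / 0.0976 = 0.00, so power is 50%.

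The same steps for other week-8 response rates give:

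| Week-8 response, naive / experienced | All-treated rates | All-treated power | Responder-only power |
|---|---|---|---|
| 80% / 65% | 40.0% v 19.5% | 73% | 50% |
| 78% / 70% | 39.0% v 21.0% | 61% | 52% |
| 75% / 75% | 37.5% v 22.5% | 46% | 53% |

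In the last row naivety does not affect week-8 response, and the responder-only test has the higher power.

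**Subjects lost to the restriction.** At the 75% planning rate, 0.75 × 139 = 104 remain, so about a quarter are excluded.

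**How far an all-treated test would help.** For 40.0% versus 32.5%, SE0 = 0.0835 and SE1 = 0.0825. (0.075 − 0.164) / 0.0825 = −1.07, so power is about 14%. The 95% interval for the 7.5-point difference has a half-width of 1.96 × 0.0825 = 16.2 points.

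**The case against.** The responder denominator was not invented for this block. The protocol's primary and secondary endpoints (section 9.1) set the week-56 outcomes among week-8 responders, and the week-56 ITT set is defined the same way. Protocol 9.1 and 9.3 describe continuation and follow-up only for responders. Under protocol 9.2.2 a patient who stops adalimumab gives no further effectiveness data. Items (5)-(8) apply that denominator by subgroup and state it each time. All of this stands, and it is why the restriction should not be called an error or removed.

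Item (4) may already supply part of what is missing. If its denominator is all treated patients, week-8 non-responders count as failures and a long-term response comparison in the whole cohort is already planned. If it follows the week-56 ITT set, it is restricted like the others. The text does not settle which, and it covers response only, not remission, steroid-free outcomes or mucosal healing.

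The all-treated test also includes the week-8 difference that item (4) tests separately, so the two comparisons answer different questions. In the example above the all-treated test would usually miss the difference as well.

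A reader might infer that the restriction costs these tests about half their power. The documents do not support that. They give no group split and no rates by group. The restriction removes about a quarter of the sample at the planning rate, and under plausible assumptions power can rise or fall.

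**Conclusion.** The point holds as a matter of what is being estimated. In SAP 6.5(5)-(7) at weeks 24 and 56, and in 6.5(8) at week 56, the naivety tests condition on a post-baseline outcome that the SAP itself relates to naivety. They describe maintenance among responders and can show no difference while all-treated rates differ, as in the assumed 50% versus 50% against 40.0% versus 32.5%.

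The size of the effect on power is unknown. With 83 and 56 treated and remission among responders of 50% versus 30%, all-treated versus responder-only power is 73% versus 50% if week-8 response is 80% / 65%, and 46% versus 53% if it is 75% in both groups. All of these rates are assumptions.

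Two broader readings should be avoided. The point does not cover all of items (4)-(8) at both visits, since item (4) states no restriction and item (8) has no week-24 test. Nor does it show the responder-only comparisons to be invalid. The analyses are exploratory and the conditioning is visible in the text, so this is a cheap improvement and not a required correction.

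**What to change.** - **Keep and label.** Keep the responder-only comparisons in SAP 6.5(5)-(8), and label them in the text and tables as conditional on week-8 response.
- **Add.** In the same items, compare naive with experienced among everyone dosed at least once, counting week-8 non-responders as not achieving the outcome. Report a risk difference with a 95% confidence interval. Given the precision shown above, the interval will say more than the p-value.
- **Write the rule down.** SAP 6.6 provides carry-forward for the partial Mayo items and no replacement for the endoscopic subscore, and SAP 6.3 excludes subjects with uncollected Mayo items. State in 6.6 that, for this analysis, the non-responder rule takes precedence. Say also how a dosed patient with no week-8 assessment is counted.
- **Settle the denominator elsewhere.** State the same all-treated denominator for 6.5(4) and for the week-56 models in 6.5(1), because SAP 2.5.1 would otherwise limit both to week-8 responders.

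The cost is SAP wording and one more column per table, with no new data. The all-treated percentages will be lower than the responder-only ones, so the two columns need clear titles.
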